NCT: 04952909

Protocol title: A Prospective, Multicenter, Non-Randomized, Single-Arm, Open-Label Clinical Study to Demonstrate the Safety and Effectiveness of the ShortCut[™] device (The ShortCut[™] Study).

Document date: 17/Apr/2023

The ShortCut[™] Study Protocol Synopsis

1 Full title

A Prospective, Multicenter, Non-Randomized, Single-Arm, Open-Label Clinical Study to Demonstrate the Safety and Effectiveness of the ShortCut[™] device (The ShortCut[™] Study).

2 Device name

ShortCut™

3 Design

This is a prospective, multicenter study sponsored by Pi-Cardia Ltd. This clinical study is aimed to demonstrate safety and effectiveness of the ShortCut[™] device for splitting bioprosthetic aortic valve leaflets, and to demonstrate coronary artery ostia patency following leaflet split, in patients who are presented for a valve-invalve (ViV) transcatheter aortic valve replacement (TAVR) procedure, and who are at risk for TAVR-induced coronary artery obstruction.

4 Objective

To assess the safety and effectiveness of the ShortCut[™] device for splitting bioprosthetic aortic valve leaflets, and to demonstrate coronary artery ostia patency following leaflet split, in patients who are at risk for TAVR-induced coronary artery obstruction following a ViV procedure.

5 Endpoints

5.1 Primary endpoints

5.1.1 Primary safety endpoint

Each of the following ShortCut[™] device and/or ShortCut[™] procedure-related serious adverse events will be assessed at discharge or at 7 days post-procedure, whichever occurs first:

- Mortality
- Stroke (fatal, disabling and non-disabling)

5.1.2 Primary effectiveness endpoint

Overall leaflet splitting success using the ShortCut[™] device assessed intra-procedurally by echocardiography and or angiography.

Per patient leaflet splitting success will be determined as follows:

- For patients in whom one leaflet was intervened, splitting success per patient will be determined based on the splitting success of the intervened leaflet:
 - Visualization of leaflet split, assessed by intraprocedural TEE immediately post-ShortCut[™] procedure and prior to TAVR, OR
 - Increase in aortic regurgitation from pre to post leaflet split, assessed by intraprocedural TEE or angiography.
- For patients in whom two leaflets were intervened, splitting success per patient will be determined based on the splitting success of the first intervened leaflet.

5.2 Secondary endpoints

5.2.1 Secondary safety endpoints

The following events will be assessed through 30 days post index procedure (according to VARC-3):

- All-cause mortality
- All-cause stroke (fatal, disabling and non-disabling)
- Coronary obstruction
- Myocardial infarction with new evidence of coronary artery obstruction requiring intervention
- Major vascular complications
- Cardiac tamponade
- Acute kidney injury¹
- Access-related type 3-4 bleeding

5.2.2 Secondary effectiveness endpoints

- Per intervened leaflet splitting success will be assessed intra-procedurally and will be determined based on the splitting success of this leaflet:
 - ∨ Visualization of leaflet split, assessed by intraprocedural TEE immediately post-ShortCut[™] procedure and prior to TAVR, OR

¹ Acute kidney injury (AKI, VARC-3):

[•] Increase in serum creatinine >300% (>3.0 X increase) within 7 days compared with baseline

[•] Serum creatinine \geq 4.0 mg/dL (\geq 354 mmol/L) with an acute increase of \geq 0.5 mg/dL (\geq 44 mmol/L)

AKI requiring new temporary or permanent renal replacement therapy

- Increase in aortic regurgitation from pre to post leaflet split, assessed by intraprocedural TEE or angiography.
- The following endpoints will be assessed through 30 days post index procedure:
 - Freedom from coronary artery ostia obstruction related to the intervened leaflet
 - Freedom from coronary artery intervention related to the intervened leaflet

5.2.3 Technical success endpoint

A composite of the following, which will be assessed at exit from procedure room following the ShortCut[™] procedure:

- Successful access, delivery, and retrieval of the ShortCut[™] device
- Freedom from ShortCut[™] device- and/or ShortCut[™] procedure-related mortality
- Freedom from ShortCut[™] device- and/or ShortCut[™] procedure-related:
 - Surgery or intervention
 - Major vascular or access-related complications
 - Cardiac structural complication

5.3 Tertiary safety endpoints

The following events will be assessed through 90 days post index procedure (according to VARC-3):

- All-cause mortality
- Stroke
- Myocardial infarction with new evidence of coronary artery obstruction requiring intervention.

6 Patient population

Patients who are planned to undergo a percutaneous valve-in-valve (ViV) procedure for an approved ViV indication, and who are at risk for TAVR-induced coronary artery ostium obstruction, according to the local Heart Team decision.

7 Eligibility Criteria

7.1 Inclusion criteria

1. Male or female \geq 18 years of age at the time of screening.

- 2. Patient is planned to undergo a percutaneous valve-in-valve procedure for an approved ViV indication due to a failed bioprosthetic valve.
- 3. Patient is at risk for TAVR-induced coronary artery ostium obstruction.
- 4. Written informed consent to participate in the study obtained from the subject or subject's legal representative, according to local regulations, prior to initiation of any study mandated procedure.

7.2 Exclusion criteria

- An excessive aortic valve leaflet Calcium morphology, such as diffuse massive calcification at the targeted leaflet for splitting or anatomy not suitable for the use of the ShortCut[™] device, as determined by the CT core lab.
- 2. Leaflet planned to be intervened is torn pre-ShortCut device access.
- 3. Patient has iliofemoral vessel characteristics that preclude safe insertion of the introducer sheath.
- 4. Anatomy that does not allow safe placement of a cerebral embolic protection device.
- 5. Planned concurrent intervention in the same setting of the index procedure.
- 6. Surgery or interventional procedure ≤ 1 month prior to the index procedure.
- 7. Planned provisional (pre-position coronary artery) stents.
- 8. Coronary disease that, in the opinion of the local Heart Team, should be treated; or treatment of coronary disease ≤ 1 month prior to index procedure.
- Carotid or vertebral artery disease that, in the opinion of the local Heart Team, should be treated; or treatment of carotid stenosis ≤ 1 month prior to index procedure.
- 10. CVA or TIA \leq 6 months prior to index procedure.
- 11. Severe neurological disability, as determined by the Investigator.
- 12. History of a myocardial infarction (MI) ≤ 6 weeks prior to index procedure.
- 13. Current or suspected endocarditis on the aortic valve.
- 14. Identified thrombotic material on the valve by either CT or Echocardiography.
- 15. Cardiac imaging evidence of left ventricular intracardiac mass or thrombus.
- 16. Hemodynamic or respiratory instability requiring inotropic support, mechanical ventilation or mechanical heart assistance.
- 17. LVEF < 30%.
- 18. Ongoing severe infection or sepsis.
- **19**. Known current COVID-19 infection (with or without symptoms), recent positive test for COVID-19, or recent exposure to a person with COVID-19 infection.

- 20. Patient refuses blood transfusion.
- 21. Patient has renal insufficiency (GFR < 30 ml/min or serum creatinine > 2.5 mg/dL), or on chronic dialysis.
- 22. Patient with clinically significant abnormality in cell blood count as defined by WBC < 3000 cell/ μ L, Hb < 9 g/dL and platelet count < 90,000 cell/ μ L or history of bleeding diathesis or coagulopathy, or hypercoagulable states.
- 23. Active peptic ulcer with bleeding.
- 24. Known allergy to contrast media that cannot be adequately controlled with premedication.
- 25. Known hypersensitivity or contraindication to all intra-procedural anticoagulation or any product material (Nitinol alloys, stainless steel, Polyamide 12, Polyether block amide, Polytetrafluoroethylene (PTFE, Teflon), Polyphenylsulfone (PPSU), Polyvinyl chloride (PVC, DEHP Free), Polypropylene (PP), SurModics Serene coating (PhotoLink[®] surface modification), Silicone, Epoxy adhesive, Acrylic glue).
- 26. Pregnant women or women planning a pregnancy within 1 month of study enrollment.
- 27. Need for emergency surgery for any reason.
- 28. Inoperable for emergency open-heart surgery.
- 29. Patient has a condition that, in the opinion of the Investigator or the Screening Committee, precludes the patient from undergoing the index procedure.
- 30. Life expectancy is less than one year.
- 31. Patient is currently participating in another investigational drug or device study. Note: Studies requiring extended follow-up for products that were investigational, but have since become commercially available, are not considered investigational studies. Observational studies are not considered exclusionary.
- 32. Patient is unwilling to participate or unwilling to return for study follow-up activities.
- 33. Patient is unable to consent to participate, unless the subject has a legally authorized representative.

8 Study schedule and time points

	Screening	Baseline	Index procedure	Pre- discharge	30 days post- procedure	90 days post- procedure
Informed consent	Х					
Medical and surgical history review	Х	Х				
NYHA classification	Х				Х	
Risk assessment, including	Х					
EuroSCORE II and STS score						
Physical examination		Х			Х	
Blood tests ¹		Х		Х		
12-lead ECG	Х	Х		Х	Х	
Modified Rankin Score and NIHSS ⁸		Х		X ⁷	X ⁷	
5 Meters-Walk Test		Х				
Katz Activities of Daily Living (ADL)		Х				
CT of heart, aortic root, and aortic	X ²					
arch						
Echocardiographic imaging	X ³	X ⁵	X ⁶	Х		
Invasive or CT coronary angiography	X ⁴					
ShortCut [™] assisted TAVR			Х			
Angiography for coronary patency			Х			
Adverse events recording		Х	Х	Х	Х	Х
Medications recording		Х	Х	Х	Х	Х
Clinical status remote evaluation						Х

¹ The relevant blood assays are listed above in each timepoint section.

² CT scan will be performed only in case no adequate CT scan was performed within 6 months prior to screening.

³ TTE at screening will be performed only in case no adequate TTE was performed within 90 days prior to screening.

⁴ Invasive or CT coronary angiography will be performed only in case no invasive or CT coronary angiography was performed within 1 year prior to screening, or the patient had new ischemic symptoms since last invasive or CT coronary angiography.

⁵ TTE at baseline will be done in case no adequate TTE was performed within 30 days prior to index procedure.

⁶ Intra-procedure TEE will be performed during the ShortCut[™] procedure.

⁷ Modified Ranking Score and NIHSS assessments shall be done only for patients who had a suspected neurological event.

⁸ In the event a patient experiences a stroke event within 30 days post index procedure, an additional visit at 90 days after the onset of event will be performed and will include Modified Ranking Score and NIHSS assessments.

9 Statistical Analysis Plan

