9.1 Study Analysis Sets

9.1.1 Safety analysis set

The safety analysis set will include all patients who reached the point of index procedure, i.e., patients in whom the ShortCut[™] device was introduced through the introducer sheath. Patients who were treated with the ShortCut[™] without meeting the eligibility criteria will also be included in this analysis set.

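### Exclusion 22 joins its white-cell, haemoglobin and platelet limits with *and*, so read literally an isolated severe anaemia or thrombocytopenia does not exclude a patient under that item

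*Combined protocol and SAP*

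**What the plan says.** Section 7.2 of the combined protocol and SAP lists the exclusions. Item 22 opens with "Patient with clinically significant abnormality in cell blood count as defined by WBC < 3000" cells per µL. After a comma it continues "Hb < 9 g/dL and platelet count < 90,000" cells per µL, and then adds "or history of bleeding diathesis or coagulopathy, or hypercoagulable states". The three blood-count limits are therefore one list closed by *and*, while each history condition is introduced by *or*.

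Three other places bear on the point:

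- Item 21, directly above, joins its laboratory limits with *or*: "Patient has renal insufficiency (GFR < 30 ml/min or serum creatinine > 2.5 mg/dL), or on chronic dialysis".
- Item 29 is a general exclusion by judgement: "Patient has a condition that, in the opinion of the Investigator or the Screening Committee, precludes the patient from undergoing the index procedure".
- Section 5.2.1 includes "Access-related type 3-4 bleeding" among the secondary safety endpoints.

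**The concern.** Item 22 gives a separate threshold for each of three cell lines, which suggests that each was meant to work alone as a safety limit. The connector makes them work only together. A site that follows the text exactly could accept a patient with one severe abnormality, such as marked anaemia, as long as the other two counts are acceptable and there is no relevant history.

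The study procedure is invasive and requires an introducer sheath in the iliofemoral vessels (item 3). The plan itself treats bleeding as a risk to be tracked, and item 20 excludes patients who refuse transfusion. At stake are the safety of individual patients at enrolment and consistency between sites, since two sites could decide differently on the same patient. It is also unclear whether enrolling someone with, say, Hb 8 g/dL alone breaches eligibility.

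**Working it through.** The plan gives no figure to reproduce here. The check is to read item 22 as a logical rule and see which patients it catches.

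**Inputs (section 7.2, item 22).** Let W be WBC < 3000 cell/µL, H be Hb < 9 g/dL, P be platelets < 90,000 cell/µL, and D be any of the history conditions.

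- As written: excluded if (W and H and P) or D.
- Probable intent: excluded if W or H or P or D.

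**Test cases with no such history (D false).**

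- Hb 7 g/dL, other counts normal: H is true, W and P are false. As written, not excluded. With *or*, excluded.
- Platelets 50,000, other counts normal: P is true, W and H are false. As written, not excluded. With *or*, excluded.

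**All patterns with D false.** Three limits give 2³ = 8 patterns, of which 8 − 1 = 7 have at least one breach.

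| W | H | P | *and* (as written) | *or* |
|---|---|---|---|---|
| no | no | no | not excluded | not excluded |
| yes | no | no | not excluded | excluded |
| no | yes | no | not excluded | excluded |
| no | no | yes | not excluded | excluded |
| yes | yes | no | not excluded | excluded |
| yes | no | yes | not excluded | excluded |
| no | yes | yes | not excluded | excluded |
| yes | yes | yes | excluded | excluded |

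The written rule excludes 1 of the 7, and *or* excludes 7 of 7. The readings differ on 7 − 1 = 6 patterns: 3 single and 3 double breaches.

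**Does another criterion fill the gap?**

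- The history conditions in item 22 still work, because they are joined by *or*. They may catch some patients with low platelets, but only where such a history exists. They do not cover isolated anaemia.
- Items 18 (severe infection or sepsis), 20 (transfusion refusal) and 23 (bleeding ulcer) overlap in part but set no blood-count limit.
- Item 29 is discretionary and sets no number.
- In the section 8 schedule, blood tests first appear at baseline, not at screening. The document does not say which results the Screening Committee sees, so it does not show that committee review would reliably catch these patients.

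**Does it reach the analyses?** Not the main ones. The safety set (section 9.1.1) keeps patients treated with the device "without meeting the eligibility criteria will also be included in this analysis set". The primary effectiveness set (section 9.1.2) depends on a split attempt and adequate imaging. The target of 60 evaluable patients and the 75% performance goal do not depend on item 22. I claim no effect on the per-protocol sets.

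**The case against.** The strongest reply is that the wording is ambiguous rather than wrong. A list that gives one cut-off per cell line can be closed by *and* without meaning that all must fail together. *Or* was very probably intended, and many sites would read it that way. Harm would require a site to take the joint reading, find a severe single abnormality and proceed, with neither the investigator nor the Screening Committee using item 29.

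Much of this stands, and it is why the point is minor. It does not repair the rule. Item 22 presents the three limits as a definition, and discretion is no substitute for a numeric limit.

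Other objections also have some force:

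- **Item 21 is an imperfect comparison.** It joins two measures of one organ's function, whereas item 22 covers three cell lines. It shows only that *or* is used nearby for alternative laboratory limits.
- **The link to bleeding is clinical reasoning.** The document does not derive it, and it has no evident bearing on the white-cell limit.
- **Fuller protocol text may exist.** The document is headed as a synopsis. A schedule footnote refers to assay lists, and section 9.2 refers to a section 8.2.1.2; neither is present. That text might clarify item 22 or might not. The finding is limited to the text available, and unseen text cannot be relied on to correct a written criterion.
- **The pattern count is not an effect size.** That is correct. It only shows how far the two readings diverge.

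**Conclusion.** The concern holds: item 22 is wrong as written, and the point is minor. Read literally, its blood-count part excludes 1 of 7 breach patterns rather than all 7. Isolated Hb below 9 g/dL and isolated platelets below 90,000 are among the 6 that it misses. The conclusion rests on the literal reading and is confined to item 22, since item 29 could still exclude such a patient by judgement. No number of affected patients can be given, because the document reports no breach rates, and no mis-enrolment or harm has been shown. The consequence is for patient safety and consistency at eligibility, not for the trial's statistical conclusions.

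**What to change.** Reword the blood-count part of item 22 so that each limit stands alone: *WBC < 3000 cell/µL, or Hb < 9 g/dL, or platelet count < 90,000 cell/µL*. Leave the history conditions that follow unchanged. Apply this reading to all eligibility checks, so that sites and the Screening Committee use the same rule.

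The cost is a short wording clarification to one criterion and possibly a few more screen failures. The sample size, hypothesis test and analysis set definitions stay as they are.

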9.1 Study Analysis Sets

9.1.1 Safety analysis set

The safety analysis set will include all patients who reached the point of index procedure, i.e., patients in whom the ShortCut[™] device was introduced through the introducer sheath. Patients who were treated with the ShortCut[™] without meeting the eligibility criteria will also be included in this analysis set.

9.1.2 Primary effectiveness analysis set

The primary effectiveness analysis set will include the **Evaluable Patients** – patients in whom split with the ShortCut[™] device was attempted, and were determined to have Adequate Imaging to visualize split or demonstrate increase in AR according to the echo or angiography core lab. Echocardiography imaging is considered Adequate if either visualization of split or increase in AR can be assessed. Angiography imaging is considered Adequate if ncrease in AR can be assessed.

9.1.3 Secondary effectiveness analysis set

The secondary effectiveness analysis set will include patients in whom the following ShortCut[™] procedure steps have been performed: access, delivery to the aortic valve, activation of the ShortCut[™] Splitting Element and split attempt.

All intervened leaflets of these patients will be included in the secondary effectiveness analysis set.

9.1.4 Per Protocol (PP) analysis sets

9.1.4.1 Per Protocol Primary Effectiveness (PPPE) analysis set

The PPPE analysis set will include patients who are included in the primary effectiveness analysis set and who do not have major protocol violations that are likely to affect the study primary endpoints (effectiveness or safety).

9.1.4.2 Per Protocol Secondary Effectiveness (PPSE) analysis set

The PPSE analysis set will include patients who are included in the secondary effectiveness analysis set and who do not have major protocol violations that are likely to affect the study primary endpoints (effectiveness or safety).

9.2 Sample Size Considerations

The primary objective of this study is to provide accurate description of the device safety profile, and to assess its effectiveness.

The study will include up to 80 enrolled patients:

- A minimum of 60 patients for whom the ShortCut[™] procedure was initiated, split was attempted and were determined to have Adequate Imaging (Figure 1-A)
- Up to 10 additional patients for whom the ShortCut[™] procedure was initiated but:
 - o split was not attempted for any reason (Figure 1-C), or
 - split was attempted but were determined to have Inadequate Imaging (as defined in section 8.2.1.2) (Figure 1-B)
- Up to 10 additional enrolled patients who dropped out from the study prior to the index procedure (before the ShortCut[™] procedure was initiated, due to: death, consent withdrawal by patient or by physician, patient lost to follow up, or other reasons) (Figure 1-D).

The population flowchart is provided below:

Figure 1: Study population flowchart

The study is statistically powered to achieve significance for the primary effectiveness hypothesis that aims to demonstrate that the rate of Evaluable Patients with successful split is at least 75% (performance goal).

Assuming the rate of Evaluable Patients with successful split with the ShortCut[™] device is 90%, a sample size of N=60 Evaluable Patients will provide 80% power to reject the primary effectiveness null hypothesis (see section 9.4.7). The power estimation is based on an exact Binomial distribution and uses two-sided Alpha = 0.05.

To meet the performance goal of 75%, at least 52 of the 60 Evaluable Patients should have a successful split.

The study is not statistically powered to achieve significance for the primary safety endpoint. At the same time, based on pre-established event rates calculated from ViV

TAVR clinical studies, a sample size of a minimum of 60 patients for whom the ShortCut[™] procedure was initiated will allow capturing relatively rare Adverse Events (AEs), such as stroke and all-cause mortality, with high probability. The expected rates of stroke and all-cause mortality in ViV TAVR studies are estimated at 1.4% and 3.5%, respectively. The rates of stroke and all-cause mortality reported for ViV TAVR small studies (N ≤ 70) tend to be somewhat larger, and with much wider confidence intervals. Due to this difference in rate variability, a minimum of 60 patients for whom the ShortCut[™] procedure was initiated will allow demonstrating that the stroke rate (lowest of the two) does not increase more than 2-fold (i.e., more than 2.8%) compared to reported rates in ViV TAVR studies.

A sample size of a minimum of 60 patients with an initiated ShortCut[™] procedure will allow detecting at least 1 event whose incidence in the intended use patient population is 2.8% with high probability (>80%), and thus to estimate the incidence of stroke and all-cause mortality in the intended use patient population.

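### Section 9.2 says 60 initiated patients will capture stroke with high probability, but at the plan's own expected rate of 1.4% the chance of seeing even one stroke is 57%

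*Combined protocol and SAP*

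**What the plan says.** Section 9.2 of the combined protocol and SAP first states that the study is not powered for the primary safety endpoint. It then offers a different safety rationale: given pre-established event rates from ViV TAVR studies, a minimum of 60 initiated patients "will allow capturing relatively rare Adverse Events (AEs), such as stroke and all-cause mortality, with high probability". The rates follow at once: "The expected rates of stroke and all-cause mortality in ViV TAVR studies are estimated at 1.4% and 3.5%, respectively". The section adds, without a figure, that rates in small ViV TAVR studies "tend to be somewhat larger, and with much wider confidence intervals".

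Only one detection probability is quantified. It concerns "at least 1 event whose incidence in the intended use patient population is 2.8% with high probability (>80"%), and 2.8% is the value that the section introduces as twice the reported stroke rate. From this the section concludes that the incidence of both stroke and all-cause mortality can be estimated. It gives no detection probability at 1.4%.

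Stroke and mortality, restricted to events related to the device or procedure, are the two components of the primary safety endpoint (section 5.1.1).

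**The concern.** The claim names stroke and rests on rates that the plan itself supplies, yet the supporting probability is calculated at double the stroke rate. If high probability means more than 80%, as the plan's own use of the phrase suggests, the claim has to be checked at 1.4% for stroke and at 3.5% for mortality.

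What is at stake is how a result with no strokes will be read. A reader who has been told that 60 patients will very probably reveal stroke may take none as evidence that the rate is low. If none is a common result at the expected rate, that inference is unsafe. The link from seeing at least one event to estimating incidence also says nothing about how wide the interval would be.

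**Working it through.** **Inputs, all from section 9.2**
- Initiated patients: minimum 60. Adding the up to 10 who are initiated but not evaluable gives 60 + 10 = 70. The enrolment cap is 80.
- Expected rates: stroke 1.4%, all-cause mortality 3.5%.
- Two-fold stroke rate: 2 × 1.4% = 2.8%.

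**Formula.** For independent patients with a common event probability p, P(at least 1 event) = 1 − (1 − p)^n.

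**Step 1: the plan's own figure.** With n = 60 and p = 0.028, 1 − 0.972^60 = 0.818. This agrees with the stated figure of more than 80%.

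**Step 2: the expected rates with 60 patients.**
- Stroke: 1 − 0.986^60 = 0.571.
- All-cause mortality: 1 − 0.965^60 = 0.882.

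**Step 3: more patients.**

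| n | 1.4% | 2.8% | 3.5% |
|---|---|---|---|
| 60 | 57.1% | 81.8% | 88.2% |
| 70 | 62.7% | 86.3% | 91.7% |
| 80 | 67.6% | 89.7% | 94.2% |

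Even if every one of 80 enrolled patients had an initiated procedure, stroke at 1.4% would stay below 80%.

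**Step 4: where 80% is reached.**
- Rate needed with 60 patients: 1 − 0.2^(1/60) = 0.0265, and 2.65 / 1.4 = 1.9 times the expected rate.
- Patients needed at 1.4%: ln(0.2) / ln(0.986), rounded up, is 115.

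**Step 5: the likely stroke counts at 1.4% with 60 patients.**
- None: 0.986^60 = 0.429.
- Exactly one: 60 × 0.014 × 0.986^59 = 0.366.
- None or one: 0.429 + 0.366 = 0.795. Zero is the single most likely count.

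**Step 6: precision at those counts (Clopper-Pearson, two-sided 95%).**
- 0/60 = 0%, interval 0 to 6.0%; the upper limit is 1 − 0.025^(1/60) = 0.0596.
- 1/60 = 1.7%, interval 0.04% to 8.9%.

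**The case against.** The strongest reply is that the plan hides nothing. The phrase appears twice in the same argument, and the second time it carries both a probability and the incidence to which it applies. The 1.4% is printed close by, so a reader can see that 2.8% is its double. This stands in part: the quantified sentence is right, and a reader who inferred that the figure of more than 80% is an arithmetic error would be mistaken. It does not rescue the lead-in, which invokes the pre-established rates and names stroke without any condition.

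A second reply is that small studies report higher rates. The section says so but gives no figure, and describes them only as somewhat larger. The rate would have to be 1.9 times as high to reach 80%. The plan also builds its 2.8% threshold on 1.4%.

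A third reply reads stroke and mortality jointly, as at least one patient with either event. Mortality alone gives 88.2%. If the two never overlapped (an assumption, 1.4% + 3.5% = 4.9%), the figure would be 1 − 0.951^60 = 95%. But the sentence lists the two as separate examples of rare events, so this reading is possible rather than natural.

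A fourth reply is that the analysis guards against misreading. Section 9.4.3 presents the primary safety frequencies with 95% confidence intervals, section 9.4.6 adds Kaplan-Meier estimates at days 30 and 90, and no success criterion uses the detection probability. This stands and limits the harm. It does not make the sample-size statement true.

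**Conclusion.** The concern holds for stroke, and for the general claim only. At the plan's expected rate, 60 patients give a 57% chance of at least one stroke and 70 give 63%, so no stroke at all is a 43% outcome. The claim holds for all-cause mortality.

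Three stronger conclusions might be drawn, and the documents do not support them:
- That the study is too small and needs 115 patients. The plan declares that it is not powered for safety, and its effectiveness sample size does not depend on this argument. The 115 only shows how far the wording is from the design.
- That the study can give no estimate of stroke incidence. One event in 60, or none, does give an estimate; it is imprecise.
- That exactly double the expected rate is needed. The break-even is about 2.65%, slightly less than double.

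Whether 60 patients can demonstrate a stroke rate no higher than 2.8% is a separate statement in the same section, and this point does not depend on it.

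The result assumes independent patients with a common rate, and takes 1.4% as the rate that applies here. Section 9.2 states no time window for that rate and gives none for strokes related to the device or procedure. Section 9.4.3 names no interval method, so the exact method is assumed for the limits shown.

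**What to change.** Reword section 9.2 in three places:
- State that with 60 initiated patients the probability of at least one event is 57% at 1.4% (expected stroke), 82% at 2.8%, and 88% at 3.5% (expected all-cause mortality).
- Limit the high-probability claim to events with an incidence of about 2.65% or more.
- Replace the conclusion that incidence can thus be estimated with the achievable precision, giving exact two-sided 95% intervals for the two likeliest stroke counts: 0/60 = 0% (0 to 6.0%) and 1/60 = 1.7% (0.04% to 8.9%).

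This is a change of text only. It needs no more patients and alters no endpoint, analysis set, test or success rule. The cost is that one stated property of the design becomes less favourable.

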9.4.3 Primary safety analysis

The primary safety analysis will be performed on the safety analysis set. Frequency distribution of patients with ShortCut device and/or ShortCut procedure related mortality and/or stroke events, as determined by the CEC, and assessed at discharge or at 7 days post-procedure, whichever occurs first, will be presented, along with the 95% confidence intervals.

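### Section 9.2 says 60 patients can show that the stroke rate is no more than doubled (2.8%); at 95% confidence even 0 strokes in 60 leaves an upper limit of 6.0%

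*Combined protocol and SAP*

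**What the plan says.** Section 9.2 first states that "The study is not statistically powered to achieve significance for the primary safety endpoint". It then turns to what the safety sample can do all the same. Using published valve-in-valve experience, it says: "The expected rates of stroke and all-cause mortality in ViV TAVR studies are estimated at 1.4% and 3.5%, respectively". It says that at least 60 initiated patients "will allow capturing relatively rare Adverse Events (AEs), such as stroke and all-cause mortality, with high probability".

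Next comes the sentence at issue. The same 60 patients, it says, "will allow demonstrating that the stroke rate (lowest of the two) does not increase more than 2-fold (i.e., more than 2.8" per cent), measured against reported rates. The bound is twice the expected stroke rate: 2 × 1.4% = 2.8%. No confidence level is attached. The reason offered is that small published studies have higher and more variable rates.

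The following paragraph gives the only probability in this rationale: the sample "will allow detecting at least 1 event whose incidence in the intended use patient population is 2.8% with high probability (>80" per cent).

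Section 9.4.3 plans no safety test. The frequency of related death and/or stroke "will be presented, along with the 95% confidence intervals".

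**The concern.** The sentence names an upper bound and a sample size and says the second is enough to establish the first. Showing that a rate is no higher than 2.8% requires an upper confidence limit at or below 2.8%. With 60 patients and rare events, upper limits are well above that even when nothing is observed.

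The text appears to treat two different properties as one. The probability of observing at least one event when the true rate is 2.8% is a detection probability. It does not license the conclusion that the rate is below 2.8% when few or no events are seen. The greater variability of small studies, given as the reason, argues against the claim.

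What is at stake is how the safety result is described. Section 9.2 says "The primary objective of this study is to provide accurate description of the device safety profile", stroke is one of the two primary safety events (section 5.1.1), and there is no control group (section 9.3). If no strokes occur, a report could point to the plan and say that a more than two-fold increase had been excluded.

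**Working it through.** **Inputs**

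- Minimum number of initiated patients: 60 (section 9.2).
- Maximum in the planned composition: 60 + 10 = 70 initiated patients. The other 10 of the 80 are drop-outs before the procedure (section 9.2) and so fall outside the safety set (section 9.1.1). A figure for 80 is given as a ceiling, since "The study will include up to 80 enrolled patients".
- Expected rates: stroke 1.4%, all-cause mortality 3.5%; bound 2.8% (section 9.2).
- Confidence level: assumed 95%, as in sections 9.4.3 and 9.4.7. The safety section names neither method nor sidedness. I use exact (Clopper-Pearson) limits, two-sided first, following the effectiveness analysis.

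**Step 1. The plan's own figure.** P(at least 1 event) = 1 − (1 − p)^n.

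- p = 2.8%, n = 60: 1 − 0.972^60 = 81.8%. The stated figure of more than 80% reproduces.
- p = 1.4% (stroke as expected): 1 − 0.986^60 = 57.1%.
- p = 3.5% (mortality as expected): 1 − 0.965^60 = 88.2%.

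At the plan's own expected rates, capture with high probability therefore holds for mortality but not for stroke.

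**Step 2. Upper limits for the observed stroke rate.** For zero events the exact limit is 1 − 0.025^(1/n) two-sided and 1 − 0.05^(1/n) one-sided. For one event it is the corresponding beta quantile.

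| Result | Two-sided 95% upper limit | One-sided 95% upper limit |
|---|---|---|
| 0/60 | 5.96% | 4.87% |
| 1/60 | 8.94% | 7.66% |
| 0/70 | 5.13% | 4.19% |
| 0/80 | 4.51% | 3.68% |

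Every entry exceeds 2.8%. For 0/60 the ratio is 5.96 / 2.8 = 2.1. Wilson limits for 0/60, z²/(n + z²), are 6.02% two-sided and 4.31% one-sided, so the choice of method does not matter.

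**Step 3. Confidence actually available against 2.8%.**

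- 0/60: P(0 events | 2.8%) = 0.972^60 = 18.2%, so one-sided confidence is 81.8%.
- 1/60: P(at most 1 event | 2.8%) = 49.6%, so one-sided confidence is 50.4%.

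**Step 4. Size needed to exclude 2.8%.**

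- With zero strokes, two-sided 95%: ln(0.025)/ln(0.972) = 129.9, so 130 patients.
- With zero strokes, one-sided 95%: ln(0.05)/ln(0.972) = 105.5, so 106 patients.
- For 80% power at a true rate of 1.4%, find the smallest n with a cut-off c such that P(X ≤ c | 2.8%) is at most alpha and P(X ≤ c | 1.4%) is at least 0.80. This gives n = 835 (c = 14) at one-sided 0.025 and n = 691 (c = 12) at one-sided 0.05.

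**The case against.** The strongest defence has four parts.

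- **The 95% level is not in the sentence.** The only probability in this rationale is 80%, and at that level 0/60 does suffice (one-sided 80% upper limit 2.65%). This is true, but it rescues only the zero-stroke outcome: with one stroke the one-sided 80% limit is 4.91%. At the plan's expected 1.4%, zero strokes in 60 occurs 0.986^60 = 42.9% of the time, so the demonstration would fail more often than it succeeded. The plan also offers the 80% as a detection probability, not as a confidence level.
- **Section 9.2 disclaims power for safety.** It does, but the text then continues with a contrast and makes the claim anyway. The disclaimer does not withdraw it, and the two statements need reconciling.
- **Nothing depends on the bound.** This stands. Sections 9.4.3 to 9.4.6 contain no safety hypothesis, margin or decision rule, and the interval required by section 9.4.3 would show the width beside a zero count. That protection is partial: the interval covers related death and/or stroke up to discharge or day 7, and section 9.4.4 plans no interval for 30-day all-cause stroke.
- **The capture sentence names no rate of its own and should not be tested at 1.4%.** It is introduced as resting on event rates from earlier studies, and 1.4% is the stroke rate the plan then gives, so the test is fair. It remains a lesser wording point.

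It is also fair to say that no number in the passage is miscalculated. The fault is the inference drawn from a correct number.

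**Conclusion.** The concern holds. At 95% confidence, no result attainable with 60, 70 or even 80 patients shows a stroke rate of 2.8% or less; the most favourable result at the stated minimum leaves rates up to 6.0% compatible with the data. The conclusion is the same with one-sided limits and, for 60 patients, with Wilson limits. It rests on the assumption that demonstrating means 95% confidence, since the plan states no level for this claim.

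The consequence is limited. No planned analysis, sample size or success criterion changes. What should be corrected is a stated property of the design that the design does not have, in the section that justifies the safety sample.

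**What to change.** Delete the sentence claiming that the two-fold bound can be demonstrated. Keep the statement about detecting at least one event at 2.8%, which is correct, and tie the capture statement to explicit rates. Suggested replacement:

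> With 60 initiated patients, the probability of at least one stroke is 82% if the true rate is 2.8% and 57% if it is 1.4%; the probability of at least one death is 88% if the true rate is 3.5%. The exact two-sided 95% upper limit for the stroke rate is 6.0% with no strokes and 8.9% with one. The study is not designed to show that the stroke rate is at or below 2.8%.

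This changes wording in section 9.2 only. It needs no further patients and no change to a planned analysis. The price is that the stated safety precision looks less favourable. Keeping the claim instead would take at least 106 to 130 patients with no stroke at all, or roughly 690 to 835 for 80% power at the expected rate, which is a different study.
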